Study Title:

Inflammatory Indices in Predicting the Failure of Inhaled Corticosteroids Reduction in Young Participants With Asthma

NCT03788057

Document date: 25 December 2018

Objective:

Evaluation of the Usefulness of Induced Sputum Eosinophilia, eNO (exhaled nitric oxide) and Bronchial Hyperresponsiveness in Predicting the Failure of Inhaled Corticosteroids Dose Reduction in Children and Adolescents With Stable Asthma

Trial design:

A prospective, observational, interventional, single-blind study (blinded for a clinician in the field of inflammatory parameters).

Abstract:

In participants with a stable course of the asthma (confirmed in the run -in period), every 3 months the dose of ICS is halved, according to GINA (Global Initiative for Asthma) guidelines, until the control is lost or the lowest daily ICS dose is reached (200 mcg, calculated as budesonide equivalent). Throughout the treatment reduction period, the participants run an observation card (clinical symptoms) and PEFR (peak expiratory flow rate) measurements. Clinical evaluation is performed every month, with spirometry, exhaled NO and exhaled breath temperature measurements. Before the reduction and then one month after the change of treatment, the hyperresponsiveness measurement is carried out with the sputum induction (combined method using hypertonic saline), and 2 months after the change of treatment with the exercise challenge test.

In the case of loss of asthma control, beta-mimetic will be administered (temporarily) and return to dose of ICS (inhaled corticosteroid) before reduction or further increase of treatment is planned. In severe asthma exacerbations, oral steroids will be considered.

The study is observational: treatment is modified according to GINA guidelines based on clinical data as part of routine medical care. Only difference compared to standard care is supplementary inflammation evaluation (exhaled NO, sputum eosinophilia, bronchial hyperreactivity).

Introduction:

Guidelines for asthma treatment recommend using the smallest dose of ICS, which allows to maintain control of the symptoms of the disease. The GINA 2006 guidelines proposed (and later editions it upheld) that in the case of symptom control by monotherapy with ICS, to reduce their dose every 3 months, up to the lowest dose administered once a day, which should be used for one year before taking possible decision to stop it.

There are no clear and sensitive indicators that would allow detection of a threatening loss of control before the clinical symptoms worsen.

The aim of the study is the evaluation of the usefulness of induced sputum eosinophilia and other inflammatory indices [exhaled nitric oxide (NO), exhaled breath temperature (EBT), bronchial hyperresponsiveness] in predicting the failure of treatment reduction with inhaled corticosteroids in stable asthma in children and adolescents.

Methods:

This is a prospective, observational, single-blind study (blinded for a clinician in the field of inflammatory parameters). The clinician makes a decision about reducing the ICS dose based on clinical data only and is not aware of the results of the inflammatory parameters measurement.

Participants:

Participants aged 12-18 years with stable asthma (mild or moderate), treated in the Allergy Clinic of the Hospital in Lesko with medium doses in ICS. The severity of asthma was initially determined in accordance with the GINA criteria and verified during several years of observation by the assessment of clinical symptoms, functional examinations and the dose of inhaled steroids controlling the disease.

Eligibility Criteria:

Inclusion criteria:

- mild or moderate asthma with a stable course of at least 3 months:
- symptoms less than 4x per week,
- use of SABA below 3x a week,
- night awakening below 1x per week,
- FEV1 (forced expiratory volume at one second) > 80% of predicted
- no dose change in ICS or use of systemic steroids from 3 months
- good adherence to treatment

Exclusion Criteria:

- infection or exacerbation of asthma requiring the use of systemic steroids (or changes in the dose of inhaled steroids) in the last 3 months before the study
- other chronic lung diseases or general diseases affecting the respiratory system
- tobacco smoking
- FEV1 below 80% of the predicted value

Interventions:**First period (run-in):**

A four-week run-in period in which clinical symptoms and the use of short-acting beta2 agonists (SABA) and PEFR are monitored. At the end of this period, in participants with stable disease, the following parameters are measured: eNO, EBT, spirometry, and sputum induction with hyperosmolar saline in combination with hyperresponsiveness. An exercise challenge test is also performed before the reduction of treatment on another day.

The criteria for the stability of asthma in the run-in period are:

- symptoms no more than 3 times a week
- SABA is used less than 3 times a week
- no night awakening due to asthma
- PEFR variability below 20%
- FEV1 above 80% of predicted

Second period of the study - reduction of anti-inflammatory therapy.

In participants with the previously stable course of asthma (confirmed in the run-in period), asthma control is monitored regularly throughout the observation period. All participants run an observation card (clinical symptoms) and PEFR measurements. Monthly spirometry, exhaled NO and exhaled breath temperature measurements are performed. Every 3 months and one month after the change of treatment (i.e in months 0, 1, 3, 4, 6 and 7), the hyperresponsiveness measurement is carried out with the sputum induction (combined method, [7]). Two months after the dose change (months 2, 5, 8) the exercise challenge test is carried out.

Every three months, the control of the asthma symptoms is evaluated based on the clinical data, and a possible change of ICS dose is considered. The results of bronchial reactivity measurements and sputum cytology are not known to the clinician who decides on a possible ICS dose change—he is blinded to the results of tests, and the therapeutic decision is based solely on clinical evaluation.

In participants with a stable course of the disease over the past 3 months, the dose of ICS is halved, following GINA guidelines. In the case of loss of asthma control, appropriate treatment modifications are administered, and the patient is withdrawn from the study.

If control of symptoms is maintained (evaluation based on clinical symptoms solely), every 3 months the dose of ICS is halved according to GINA guidelines, until the control is lost or the lowest daily dose is reached (200 mcg, calculated as budesonide equivalent) without losing asthma control at the next visit.

In the case of loss of asthma control, beta-mimetic will be administered (temporarily) and return to the chronic administration of the previous, twice higher dose of ICS is restored (or further increase of treatment). In severe exacerbations, oral steroids will be considered.

Measurements

1. Daily clinical evaluation by the patient:
 - Symptoms score according to the Santanello` questionnaire
 - PEFR measurement
2. Every month
 - Asthma Control Test
 - Spirometry: forced expiratory flow in 1st second (FEV1), forced vital capacity (FVC), FEF25-75 (forced expiratory flow between 25% and 75% of FVC), eNO measurement
 - exhaled breath temperature measurement (EBT)
3. every 3 months
 - quality of life test (QoL, Polish version of the questionnaire), i.e. months 3, 6, 9
 - cytological evaluation of induced sputum (i.e. months 0, 1, 3, 4, 6, 7)
 - Assessment of bronchial hyperresponsiveness:
 - one month after the ICS dose reduction and then before each subsequent dose reduction in ICS ((i.e. months 0, 1, 3, 4, 6, 7) - during the sputum induction with hyperosmolar salt (combined method))
 - 2 months after each treatment reduction (i.e. months 2, 5, 8): exercise challenge test (6-minute free-running test monitored by pulse)

Criteria for loss of control [1, 6] - any of the following:

- use of bronchodilators > 5 times a week
- the need for treatment with oral corticosteroids
- PEFR decreased above 20% for two consecutive days, compared to the average run-in period. In the case of loss of asthma control, beta-mimetic will be administered (temporarily), and return to the chronic administration of the previous, twice higher dose of ICS will be restored (or further increase of treatment). In severe exacerbations, oral steroids will be considered.

Criteria for discontinuation of participation in the study

1. Loss of asthma control (treatment strategy: beta-mimetic temporarily, return to a dose of ICS before reduction or further increase of treatment; in severe exacerbations, oral steroids).
2. Lack of adherence to the recommendations or failure to report.

The centre staff has experience in obtaining induced sputum in patients with asthma

The test will be performed in conditions ensuring patient safety, with an anaesthesiologist and anti-shock kit available.

Outcomes:

Primary Outcome Measures :

The percentage of patients with loss of asthma control [Time Frame: at 9 months]

Criteria for loss of control (any of the following):

- use of bronchodilators > 5 times a week
- the need for treatment with oral corticosteroids
- PEFR decrease >20% for 2 consecutive days, compared to the average run-in period

Secondary Outcome Measures :

Change in sputum eosinophilia [Time Frame: at 1, 3, 4, 6 and 7 month]

eosinophil percentage in induced sputum compared to baseline

Other Outcome Measures:

Change in airway hyperresponsiveness to hypertonic saline [Time Frame: at 1, 3, 4, 6 and 7 month]

Airway hyperresponsiveness to hypertonic saline measured using combined method (together with sputum induction) and compared to baseline

Change in airway hyperresponsiveness (exercise) [Time Frame: at 2, 5 and 8 month]

Airway hyperresponsiveness assessed using an exercise challenge test and compared to baseline

Change in exhaled NO [Time Frame: months 1 - 8] measured monthly and compared to baseline

Change in exhaled breath temperature (EBT) [Time Frame: months 1 - 8] measured monthly and compared to baseline

Change in FEV1 [Time Frame: months 1 - 8] measured monthly and compared to baseline

Change in FVC [Time Frame: months 1 - 8] measured monthly and compared to baseline

Change in FEF25-75 [Time Frame: months 1 - 8] measured monthly and compared to baseline

Other: ICS dose reduction

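### Do the two phrases for when the ICS dose is halved give conflicting decisions at months 3 and 6?

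*Protocol*

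**What the plan says.** All references are to the protocol; its statistical analysis plan is not shown.

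- **Halving, first phrase** (Second period of the study): "In participants with a stable course of the disease over the past 3 months, the dose of ICS is halved". The same paragraph then gives the alternative: on loss of control, treatment is modified and the participant leaves the study.
- **Halving, second phrase** (same section): "If control of symptoms is maintained (evaluation based on clinical symptoms solely), every 3 months the dose of ICS is halved". This continues until control is lost or 200 mcg budesonide equivalent is reached.
- **Three-monthly evaluation** (same section, just before the first phrase): "a possible change of ICS dose is considered".
- **Abstract**: participants whose stability was confirmed in the run-in have the dose halved every 3 months "until the control is lost or the lowest daily ICS dose is reached".
- **Stability thresholds**: the inclusion criteria require "use of SABA below 3x a week". The list headed as applying to the run-in has "SABA is used less than 3 times a week".
- **Loss of control** (its own list, repeated under Primary Outcome Measures): "use of bronchodilators > 5 times a week", a need for oral corticosteroids, or a PEFR fall of more than 20% on two consecutive days.
- **Test calendar**: sputum induction with saline challenge is scheduled "Every 3 months and one month after the change of treatment (i.e in months 0, 1, 3, 4, 6 and 7". The exercise test is two months after each dose change, given as months 2, 5 and 8.

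**The concern.** Dose reduction is the intervention under study, so the rule that triggers it matters. The section states that rule in two ways and itemises neither for months 3 and 6. Stability is itemised only for entry and run-in, and control only through its loss. The two lists are not complements: short-acting bronchodilator use must be below 3 a week to be stable and above 5 to be out of control. A clinician who carried the entry list forward would hold the dose in between, and one who asked only whether control had been lost would halve it.

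A held dose would also disturb the calendar. Tests described as one or two months after a change would follow no change, so the sputum values at months 4 and 7 and the exercise values at months 5 and 8 would mix recent reductions with older ones. A participant who completed the study without an event after a withheld reduction has undergone a weaker test of the markers than one who was halved each time, and the primary percentage alone would not show the difference.

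**Working it through.** The plan gives no figure to reproduce on this point. The check applies each reading to the protocol's own thresholds and then asks which reading the text supports.

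**1. Where the readings differ.** Reading A carries the entry or run-in limit forward and halves if weekly use n < 3. Reading B halves unless n > 5. Bronchodilator and SABA counts are taken as the same thing.

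| Uses per week | A | B |
|---|---|---|
| 0 to 2 | halve | halve |
| 3, 4, 5 | hold | halve |
| 6 or more | no halving | no halving (control lost) |

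Symptoms more than 3 times a week, any night awakening, or FEV1 not above 80% would also fail the run-in list without meeting a loss criterion.

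**2. Implied change months.** 1 − 1, 4 − 1, 7 − 1 and 2 − 2, 5 − 2, 8 − 2 both give 0, 3 and 6. The disputed decisions are those at months 3 and 6.

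**3. Months since the last reduction, if a dose were held.**

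| Reductions at | Test at 4 | 5 | 7 | 8 |
|---|---|---|---|---|
| 0, 3, 6 | 1 | 2 | 1 | 2 |
| 0, 6 (held at 3) | 4 | 5 | 1 | 2 |
| 0, 3 (held at 6) | 1 | 2 | 4 | 5 |
| 0 (held at both) | 4 | 5 | 7 | 8 |

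**4. Dose difference.** The protocol says only that doses are medium, so the starting doses here are assumptions. Doses in mcg after months 0 / 3 / 6, with the floor of 200:

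| Start | Halved each time | Held at 3 and 6 |
|---|---|---|
| 400 | 200 / 200 / 200 | 200 / 200 / 200 |
| 800 | 400 / 200 / 200 | 400 / 400 / 400 |
| 1600 | 800 / 400 / 200 | 800 / 800 / 800 |

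The largest ratio is 1 from a start of 400, 400/200 = 2 from 800 and 800/200 = 4 from 1600. From 800, reading B reaches the floor at month 3 and has nothing left to halve at month 6. From 400, neither decision matters.

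**5. Which reading the text supports.**

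- The itemised stability list is headed for the run-in, and the inclusion list defines entry. Neither is said to apply later. They also differ from each other (night awakening below once a week at entry, none in the run-in), so carrying the entry thresholds forward would not give one rule.
- The run-in list includes FEV1 and PEFR variability, whereas the second phrase rests continued halving on symptoms alone. The run-in list therefore fits poorly as a definition of that decision.
- The Abstract uses both ideas in one sentence: stability confirmed in the run-in starts the sequence, and loss of control or the floor ends it. The reduction section opens with the same reference to the run-in.
- The paragraph holding the first phrase has two branches, stable or control lost. It describes no hold.
- Calling the three-monthly change a possible one does not imply a hold for unstable participants. Under reading B a further halving is also only possible, since it stops at loss of control or at 200 mcg.

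**6. The calendar.** The outcome time frames are calendar months: sputum and saline response at 1, 3, 4, 6 and 7, exercise response at 2, 5 and 8, monthly measures at 1 to 8. They settle which value enters which outcome whether or not a dose changed. The wording about time since a change describes the full three-step sequence. It would already be loose for anyone who reaches the floor early, without any hold.

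**The case for a change.** The strongest case for acting is that the first phrase speaks of the preceding 3 months, which echoes the inclusion criterion with its explicit thresholds, and that it directly follows the paragraph on the three-monthly evaluation. A reader could fairly take it as the rule for every decision. Reading B also needs an inference: maintained control is judged on symptoms, yet the loss list contains bronchodilator use, oral corticosteroids and PEFR, and no symptom count. A sentence of wording would cost almost nothing.

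Part of this stands. A stable course is not defined for months 3 and 6, and the text never says outright that stability governs entry and loss of control governs continuation. The arithmetic on 3 to 5 uses a week and on months since reduction is correct. It does not establish two rules in conflict, because one of them has to be imported from lists that the protocol ties to entry and run-in. Both phrases also defer to GINA guidelines and to routine clinical judgement, and that source is not available here, so it cannot be shown that the step-down condition is undefined in practice.

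**Conclusion.** No change to the plan follows. Read with the Abstract, the section gives one coherent sequence: stability confirmed in the run-in, then halving every 3 months until control is lost or 200 mcg is reached. This is a finding about what the text says. Whether the rule is clinically the right one is for the investigators.

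The possible disagreement is confined to 3, 4 or 5 bronchodilator uses a week, and to the other run-in items that the loss list omits, at no more than two decisions. It would need a clinician to apply the run-in list outside its stated scope. The share of participants affected cannot be derived from the protocol. The dose ratio of up to 4 requires an assumed start of at least 1600 mcg, and at 400 mcg there is no difference.

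The primary outcome is unaffected as a definition: its three criteria do not refer to dose, so a participant with a held dose and no criterion met is a non-event under either reading. Any effect on the marker analyses could go in either direction. If the dose at each visit is recorded, which is assumed here and is natural in a study of dose reduction, an analyst can count held doses and compute the time since the last reduction. That is ordinary analysis and reporting work, usually left to the statistical analysis plan. What remains is a gap in wording that a sensible reader fills.

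### The primary outcome is the percentage of the cohort losing control, and no listed outcome links a marker to later loss of control, which is what the objective asks

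*Protocol*

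**What the plan says.** The Objective, at the head of the protocol, is "Evaluation of the Usefulness of Induced Sputum Eosinophilia, eNO (exhaled nitric oxide) and Bronchial Hyperresponsiveness in Predicting the Failure of Inhaled Corticosteroids Dose Reduction"; the population is young people whose asthma is stable. The Introduction repeats it ("The aim of the study is the evaluation of the usefulness of induced sputum eosinophilia and other inflammatory indices") and adds exhaled breath temperature (EBT) to the list. It gives an early-warning rationale: "There are no clear and sensitive indicators that would allow detection of a threatening loss of control before the clinical symptoms worsen".

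Under Outcomes, the primary measure is "The percentage of patients with loss of asthma control [Time Frame: at 9 months", with three criteria, any one of which counts as loss of control. The only secondary measure is "Change in sputum eosinophilia [Time Frame: at 1, 3, 4, 6 and 7 month", explained as "eosinophil percentage in induced sputum compared to baseline". Seven other measures follow in the same form, for example "Change in exhaled NO [Time Frame: months 1 - 8] measured monthly and compared to baseline".

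The Methods and the description of the second period say that the clinician decides on ICS dose from clinical data alone, unaware of the inflammatory results. Markers are measured before the first reduction and repeatedly after it. Participants who lose control leave the study.

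**The concern.** A prediction objective is answered by a quantity that involves both a marker and the later event. The primary outcome contains the event and no marker. The other eight contain a marker or a lung-function value and no event. The level before reduction appears only as the reference from which change is measured.

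The risk is that the headline result describes how often dose reduction fails in this clinic and says nothing about whether any marker foretold it. A prediction analysis added later would not be an analysis of the declared primary outcome. Changes from baseline do suit the early-warning rationale, but as listed they are not tied to loss of control. Because participants are withdrawn when control is lost, changes at later visits also describe mainly those who have not failed.

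**Working it through.** The protocol gives no sample size, event rate or power figure, so there is no stated number to reproduce.

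**1. Count of outcomes (Protocol, Outcomes).**

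| Type | Outcomes | Number | Contains a marker? | Contains loss of control? |
|---|---|---|---|---|
| Primary | Percentage losing control | 1 | No | Yes |
| Marker changes | Sputum eosinophils, saline hyperresponsiveness, exercise hyperresponsiveness, eNO, EBT | 5 | Yes | No |
| Spirometry changes | FEV1, FVC, FEF25-75 | 3 | No | No |

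Total 1 + 5 + 3 = 9; outcomes containing both: 0. The closing line on ICS dose reduction has no measure or time frame and reads as an intervention label, so it is not counted.

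**2. Do the listed outcomes determine predictive value?** By construction a cohort percentage cannot. A simulation shows the same for the change scores. Assumptions, none from the protocol: standard-normal marker change, 20% or 40% failing, latent marker-failure correlation 0, 0.5 or 0.9.

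| Failing | Mean (SD) of change | AUC at correlation 0 / 0.5 / 0.9 |
|---|---|---|
| 20% | 0.00 (1.00) | 0.50 / 0.75 / 0.95 |
| 40% | 0.00 (1.00) | 0.50 / 0.73 / 0.94 |

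The same failure percentage and the same mean change fit a useless marker and a nearly perfect one.

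**3. What a restated primary would deliver.** Hanley-McNeil variance for AUC = A, with m failures and n non-failures:

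Var = [A(1−A) + (m−1)(Q1−A²) + (n−1)(Q2−A²)] / (mn), where Q1 = A/(2−A) and Q2 = 2A²/(1+A).

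For A = 0.75: Q1−A² = 0.6000 − 0.5625 = 0.0375 and Q2−A² = 0.6429 − 0.5625 = 0.0804. With an assumed 30% failing:

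- 30 participants (9/21): (0.1875 + 8×0.0375 + 20×0.0804)/189 = 0.0111; SE 0.105; half-width 1.96×SE = 0.206.
- 60 participants (18/42): (0.1875 + 17×0.0375 + 41×0.0804)/756 = 0.00545; SE 0.074; half-width 0.145.
- 100 participants (30/70): (0.1875 + 29×0.0375 + 69×0.0804)/2100 = 0.00325; SE 0.057; half-width 0.112.

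With 60 participants and 20% to 50% failing, the half-width runs from 0.171 to 0.124.

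**4. How far such a result separates markers.** With 18 of 60 failing, the present primary reads 30% (Wilson 95% CI 20% to 43%) whatever the AUC. The restated one reads 0.50 ± 0.16 for an uninformative marker and 0.90 ± 0.10 for a strong one. With 9 of 30 and a moderate AUC of 0.70, the half-width is 0.22, giving 0.48 to 0.92. That includes 0.50 and overlaps the 0.27 to 0.73 of the uninformative case.

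**5. Window.** A fixed 9-month end gives a month-0 value a horizon of 9 months, a month-3 value 9 − 3 = 6 and a month-6 value 9 − 6 = 3. Values before later reductions therefore need a window that ends at the next scheduled decision. As an illustration, take 60 participants, two steps with 9 failures each, and every controlled participant reduced again: 60 + 51 = 111 records, 18 failures and 93 non-failures. At AUC 0.75 the half-width is 0.137, ignoring repeated records per participant. This is close to the 0.145 above, so the choice of window matters little for precision.

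**The case against.** The best defence is that in a prediction study the event is the outcome and the markers are predictors, and the measure joining them is an analysis choice. The protocol defines the event explicitly, names the candidate markers, schedules them before and after reduction, and blinds the clinician. The Objective itself supplies the intended link. A SAP that is not shown may settle predictor form, visit, cut-offs and model.

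Much of this stands. The absence of a model, a cut-off or a ROC method is not a fault here. A reader might infer that the study cannot answer its question, or that the wrong data are collected. The documents do not support that: loss of control is the right event, the markers are the right candidates, and both are available for each participant. What the defence does not remove is that naming the primary outcome is the protocol's job, and the one it names is a cohort percentage.

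A reader might also infer that the pre-reduction level must be the main predictor. The documents do not settle this. The early-warning rationale and the only secondary outcome point at least as much to change after reduction.

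Finally, one might infer from the contrast of AUC 0.50 with 0.90 that the restated outcome would cleanly sort good markers from poor ones. It would not do so for moderate markers in a small cohort, as step 4 shows.

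**Conclusion.** The point holds as a mismatch between the objective and the declared outcomes, and it should be fixed. None of the nine listed outcomes joins a marker to later loss of control, so the primary result as written does not address the objective. That conclusion rests on the text alone. Every AUC, interval and simulated figure rests on assumed cohort sizes, failure rates and timing; they illustrate consequences and do not measure a defect in this protocol. The lead marker (sputum eosinophils, named first in the aim and the only secondary outcome) and the 9-month frame are already signalled, so the repair is small.

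**What to change.** Restate the primary outcome as the association or discrimination, for example AUC with 95% CI, between sputum eosinophil percentage and subsequent loss of control by the existing criteria. Fix one predictor form and one matching window in the protocol before analysis:

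- **Simplest:** the month-0 value before reduction against loss of control by 9 months, one record per participant.
- **If values before later reductions (months 3 and 6) are used:** the interval to the next scheduled decision, so that horizons are equal.
- **If the authors prefer change after reduction,** in line with the Introduction: that change as predictor of later loss of control only, among those still controlled at that visit.

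Make the same measure secondary for eNO, EBT and hyperresponsiveness. An exercise test is already planned before the first reduction. For later steps the latest available test is the one at month 2 or 5, since "Two months after the dose change (months 2, 5, 8) the exercise challenge test is carried out". Keep the 9-month percentage and the changes from baseline as descriptive outcomes, and leave model details, including repeated records, to the SAP.

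The cost is outcome wording and analysis; no new measurement is needed and the criteria for loss of control are unchanged. The percentage losing control is no longer the headline, and the precision of the new one depends on a number of failures that the protocol does not state.
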